### 6.5.1. Primary efficacy analysis

#### Treatment's success rate.

Duration of crying will be collected daily in the diary during the entire study period. The average daily duration will be defined as the mean duration of all cries recorded during the day in the “Evaluation of crying” section (i.e. sum of episodes’ duration/number of cries during the day).

Weekly mean will be defined as the mean of the calculated average daily durations during the selected week and will be described by means of descriptive statistics for continuous data. Mean changes from baseline (i.e. mean of the first Week) to the mean of the selected week will be computed as well.

Treatment success rate will be evaluated in terms of reduction of duration of cries, comparing mean weekly duration of the last Week (from T4 to T5) and mean weekly duration of Week 1 (from T0 to T1). A success will be defined as a reduction  $\geq 50\%$ .

The proportion of patients with a success in the two groups will be summarized by means of descriptive statistics for categorical data and analyzed by means of a Chi-Square test.

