## Statistical Analysis Plan

Sponsor:

Protocol number:

Moreover, in order to compare the two groups of patients, a t-test on the change of weekly mean of cries at last Week will be performed. In case of data not normally distributed, a Wilcoxon/Mann-Whitney test will be used.

- Number of infections of the respiratory system, gastrointestinal system, urinary system or skin during the study period.

Number of infections will be described on the ITT population, even if infections are defined using safety parameter. In fact, an infection will be defined as an Adverse Event with SOC equal to "Infections and Infestations".

The frequency and proportion of patients who reported at least one infection will be summarized and presented by category, System Organ Class and Preferred Term.

- Evacutive frequency

Frequency and consistency of stools are collected daily in the diary.

Stool frequency will be evaluated as the mean of total daily stools reported per week. Mean changes from baseline (i.e. mean of the first Week) to the mean of the selected week will be analyzed.

Summary statistics of mean stool frequency per week will be provided by means of descriptive statistics for continuous data.

- Consistency of the fecal mass

Stool consistency will be evaluated as the number and the proportion of patients who reported at least one stool sample of each type per week, according to Bristol scale. Patients could report more than one stool consistency per day (according to the number of daily stools): all the information collected will be analyzed.

Other data from patients' diary will be analyzed:

- Infant's mood

Infant's mood (calm, asleep, agitated, irritable) is collected daily in the diary and will be evaluated as the number and the proportion of infants who reported at least one mood of each type per week.

- Infant's sleep

Duration of sleep (in minutes) will be collected daily in the diary during the entire study period. The average daily duration will be defined as the mean duration of all sleeps during the day (i.e. sum of episodes' duration/number of sleeps during the day).

Weekly mean will be defined as the mean of the calculated average daily durations during the selected week and will be described by means of descriptive statistics for

	Statistical Analysis Plan
	Sponsor:
	Protocol number:

continuous data. Mean changes from baseline (i.e. mean of the first Week) to the mean of the selected week will be analyzed too.

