- **Infant's temper**

Duration of temper episodes (in minutes) will be collected daily in the diary during the entire study period. The average daily duration will be defined as the mean duration of all temper episodes during the day (i.e. sum of episodes' duration/number of temper episodes during the day).

Weekly mean will be defined as the mean of the calculated average daily durations during the selected week and will be described by means of descriptive statistics for continuous data. Mean changes from baseline (i.e. mean of the first Week) to the mean of the selected week will be analyzed as well.

- **Infant's feeding**

Feeding time (in minutes) will be collected daily in the diary during the entire study period. The average daily duration will be defined as the mean feeding time during the day.

Weekly mean will be defined as the mean of the calculated average daily durations during the selected week and will be described by means of descriptive statistics for continuous data. Mean changes from baseline (i.e. mean of the first Week) to the mean of the selected week will be analyzed also.

Information about way of feeding will be only listed.

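### SAP 6.5.3 labels sleep and temper as average daily duration but computes minutes per episode, so these descriptive summaries can miss or reverse a change in daily time

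*SAP*

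**What the plan says.** Sleep and temper are introduced in SAP 6.5.3 after the listed secondary variables, under the line "Other data from patients' diary will be analyzed".

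- **Sleep.** The raw data are minutes: "Duration of sleep (in minutes) will be collected daily in the diary during the entire study period". The derived variable follows: "The average daily duration will be defined as the mean duration of all sleeps during the day", with the formula given as "sum of episodes' duration/number of sleeps during the day".
- **Temper.** "The average daily duration will be defined as the mean duration of all temper episodes during the day", with the formula "sum of episodes' duration/number of temper episodes during the day".
- **Weekly value, both variables.** "Weekly mean will be defined as the mean of the calculated average daily durations during the selected week". Week 1 is the baseline. Descriptive statistics are planned for the weekly means, and changes from Week 1 are to be analyzed. No between-group test is named.

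SAP 6.5.3 plans no total of sleep or temper minutes per day and no count of sleep or temper episodes. SAP 6.1 marks the handling of missing data as not applicable, and neither entry says what to do with a day that has no episodes.

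**The concern.** The label promises time per day, but the formula delivers time per episode. The two differ by a factor equal to the number of episodes, and that number may itself change during treatment. An infant whose temper episodes become fewer but stay the same length shows no change on the planned measure. If the short episodes disappear first, the measure gets worse while daily temper time falls. For sleep, an infant who sleeps longer in total but in more, shorter stretches would appear to sleep less.

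A reader of a table headed *average daily duration* would take it as minutes per day and could not correct it from the other planned output. What is at stake is the interpretation of those descriptive tables.

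**Working it through.** The documents give no figure for sleep or temper, so there is no stated result to reproduce. The planned 33 infants per group (SAP 3.6) belongs to the primary endpoint and plays no part here. The check is algebraic, and the episode patterns below are assumptions chosen for illustration, not trial data.

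**Step 1: what the formula measures.** Let T be total minutes in a day and k the number of episodes that day. The planned daily value is T/k, in minutes per episode. The quantity that the label suggests is T.

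**Step 2: how the two can diverge.** If T changes by a proportion t and k by a proportion g, the planned measure changes by (1 + t)/(1 + g) − 1.

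- If g = t, the result is 0 and the change in daily time is missed.
- If g has the same sign as t and is larger in size, the result has the opposite sign to t and the change is reversed.

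**Step 3: illustrations.** Each row assumes the same pattern on every day of the week, so the weekly mean equals the daily value.

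| Pattern (episodes × minutes) | Daily total, min | Change in total | Planned measure, min | Change in measure |
|---|---|---|---|---|
| Temper 6×20 to 2×20 | 120 to 40 | −67% | 20 to 20 | 0% |
| Temper 6×20 to 2×30 | 120 to 60 | −50% | 20 to 30 | +50% |
| Sleep 12×60 to 14×60 | 720 to 840 | +16.7% | 60 to 60 | 0% |
| Sleep 8×90 to 12×70 | 720 to 840 | +16.7% | 90 to 70 | −22.2% |

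Check of the second row with the formula: t = −1/2 and g = 2/6 − 1 = −2/3, so (1/2)/(1/3) − 1 = +50%.

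**Step 4: temper days without episodes.** Here T = 0 and k = 0, so T/k is undefined. Suppose Week 1 has three 20-minute episodes every day (60 min/day, 20 min per episode). Suppose the last week has six days without temper and one day with a single 40-minute episode.

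- Daily total: 40/7 = 5.7 min/day, a change of 5.7/60 − 1 = −90%.
- Planned measure if empty days are dropped: 40 min, a change of 40/20 − 1 = +100%.
- Planned measure if empty days are set to 0: 40/7 = 5.7 min, a change of 5.7/20 − 1 = −71%.

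The direction of the result thus depends on a rule that the SAP does not state.

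**Step 5: comparison within the plan.** In the same section, stool frequency is derived from daily totals averaged over the week, so the SAP does use daily totals where it wants a daily quantity. The primary endpoint in SAP 6.5.1 uses the per-episode construction: "sum of episodes’ duration/number of cries during the day".

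**The case against.** **No planned conclusion rests on these variables.** Sleep and temper are absent from the protocol's objectives and evaluation criteria, from SAP 2.1 and 2.2, and from the variable list in SAP 5.1. They have no named between-group test, unlike the number of cries. This stands, and it limits the weight of the point.

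**The formula is disclosed, so the fault is mainly the label.** This stands in part. A reader of the SAP can see that the quantity is per episode, but a reader of the output table may not. Relabelling alone would still leave daily time unreported.

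**Mean sleep-episode length is informative in itself.** It can be, and there is no reason to discard it. The SAP gives no such rationale, however, and does not name the measure that way. Nor does the idea that fewer episodes mean improvement carry over from temper: fewer sleeps of equal length would be less sleep.

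**Zero-episode days might not be dropped.** A reader might infer that the plan removes the best temper days from the weekly mean. The documents do not say so. Dropping is a natural result of 0/0, and the number-of-cries rule in SAP 6.5.3 divides by days with episodes. Against that, the protocol synopsis (statistical methods, primary variable) includes zero values, although only for crying duration. What can be said is that no rule is given for temper.

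**The illustrations are invented.** This is correct. They prove that a missed or reversed change is possible; how likely it is cannot be judged from the documents.

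**Conclusion.** The point holds as a defect of derivation and labelling in supplementary descriptive results. Followed exactly, SAP 6.5.3 reports mean minutes per episode under a daily label. That measure can show 0% when daily temper time falls by 67%, or +50% when it falls by 50%. For sleep it can show −22.2% when daily time rises by 16.7%. These sizes depend on the assumed episode patterns; the algebra behind them does not.

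A reader might go further and infer that the trial's efficacy conclusion is compromised by the sleep and temper derivations. The documents do not support that, because nothing confirmatory uses these variables. The same formula matters far more in SAP 6.5.1, where it determines treatment success. The sleep and temper entries are the lesser instance and are best corrected alongside it.

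**What to change.** In SAP 6.5.3, for both sleep and temper:

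1. Define daily duration as the sum of episode minutes in the day.
2. Define the weekly mean as the mean of the daily totals over completed diary days.
3. For temper, count a completed diary day with no episodes as 0.
4. For sleep, treat a day with no sleep entries as missing. In a young infant such a day is almost certainly unrecorded, and entering 0 would bias the weekly mean downward.
5. If mean episode length is still wanted, report it separately under that name, together with the number of episodes.

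Make the change at the same time as the matching one in SAP 6.5.1, so that the diary derivations agree.

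The cost is a revised derivation and its programming. The daily total is already the numerator of the planned formula, so it needs no new data. One item needs checking: the temper rule requires the diary or eCRF to separate a completed day without episodes from a blank one. The documents do not show whether it does, and SAP 1.1 notes that some planned information was not collected in the eCRF. If the two cannot be separated, state that limitation and show the weekly mean with such days counted as 0 and with them left out.

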#### **6.5.4. Exploratory efficacy analysis**

Not Applicable.

### **6.6. SAFETY EVALUATION**

Safety data will be summarized by treatment on the Safety population.

#### **6.6.1. Adverse Events**

The incidence of Adverse Events (AEs) and Serious Adverse Events (SAEs) recorded during all the study will be presented. Treatment-emergent events will be considered those AEs with an onset date after the initiation of treatment.

Non-treatment emergent adverse events (i.e. events occurring between T0 and T1) will be listed separately.

Tables reporting a general summary of AEs will be produced by treatment group specifying the number of total events and the absolute and relative frequency of patients with AEs. As

	Statistical Analysis Plan
	Sponsor:
	Protocol number:

a patient may have more than one AE, the total number of AEs could be greater than the total number of patients.

Absolute and relative frequency of patients with drug related AEs, severe AEs, SAEs, AEs with an outcome of death, AEs leading to permanent discontinuation of treatment, AEs leading to temporarily interruption, AEs leading to hospitalization/prolonged hospitalization will be also reported.

Drug-related AEs will be the AEs with causality equal to "Probably", "Possibly" and "NA"; if the relationship to study drug is unknown or missing, the AE will be drug related as well.

AEs will be tabulated by System Organ Class, Preferred Term and severity. The absolute and relative frequency of patients who have experienced each type of event will be presented; if the same patient reported more than one occurrence of the same AE with different intensity, no selection of the one with the worst intensity will be adopted.

SAEs will be summarized similarly.

All serious AEs, study drug related AEs, AEs with an outcome of death, AEs leading to permanent discontinuation of treatment will be listed with all their details.

Relative days, defined as days elapsed from the treatment start to the onset date of the event, will be computed.

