## 5.2. SAFETY VARIABLES

### Adverse Events

Adverse events are defined as the appearance of undesirable sign(s) (included laboratory abnormal values), symptom(s) or medical condition(s) temporarily associated to a drug.

An Adverse Event will be defined as a Serious Adverse Event if the event:

- results in death
- is life-threatening
- requires in-patient hospitalization or prolongation of existing hospitalization
- results in persistent or significant disability/incapacity

or

- is a congenital anomaly/birth defect

An event that compromises patient safety will be considered as a Serious Adverse Event.

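### The treatment-emergent definition has no worsening clause, so a run-in condition that worsens on product may be left out of the by-arm adverse event tables

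*SAP*

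**What the plan says.** SAP 6.6.1 (Adverse Events) gives the rule: "Treatment-emergent events will be considered those AEs with an onset date after the initiation of treatment". The next sentence deals with the remainder: "Non-treatment emergent adverse events (i.e. events occurring between T0 and T1) will be listed separately". The definition in SAP 5.2 opens with "Adverse events are defined as the appearance of undesirable sign(s" and goes on to symptoms and medical conditions. It speaks of appearance only, not of worsening.

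Other sentences in 6.6.1 are wider. The section begins "The incidence of Adverse Events (AEs) and Serious Adverse Events (SAEs) recorded during all the study will be presented". The summary by arm is worded without any limit to emergent events: "Tables reporting a general summary of AEs will be produced by treatment group specifying the number of total events". The detailed listing covers "All serious AEs, study drug related AEs, AEs with an outcome of death" and events leading to permanent discontinuation, again without such a limit. The section also foresees repeat reports of one event, "if the same patient reported more than one occurrence of the same AE with different intensity", and keeps all of them.

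Neither the SAP nor the protocol synopsis says whether a worsening is entered as a new record with its own onset date.

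**The concern.** The protocol synopsis rests safety on two things, physical examination and the incidence of adverse events. All these infants have colic at entry and are observed for a week before the first dose. In such a population, intolerance may show as the aggravation of a complaint that is already there, not only as a new one. A rule based on onset date attaches the event to the run-in, whatever happens to it on product. If the by-arm tables are then built on emergent events, aggravation that occurred after randomization is missing from the safety summary, although it is information on the product.

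**Working it through.** The plan gives no figure on this point, so there is none to reproduce. The check is a reading of the rules, followed by an illustration of size.

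**1. Applying the rule.** Suppose a complaint starts on day 5 of the run-in, treatment starts at T1 (day 7 in the SAP 3.7 flow chart), and the complaint worsens on day 12.
- Kept as one record, onset is day 5. Day 5 is before day 7, so the event is non-emergent.
- Entered as a new record, onset is day 12. Day 12 is after day 7, so the event is emergent.

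The SAP does not choose between these. The word *appearance* in 5.2 gives no support to opening a new record for worsening. The sentence on differing intensity concerns more than one occurrence, not one continuing event that gets worse.

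**2. Which tables it reaches.**

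| Recording of worsening | By-arm tables cover all AEs | By-arm tables cover emergent AEs only |
|---|---|---|
| One record | Counted, together with run-in events that did not worsen | Left out |
| New record | Counted | Counted |

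The event is lost from the by-arm tables in one cell of four. The text of 6.6.1 does not rule that cell out. If all AEs are tabulated, the emergent definition governs no stated table, and events from before randomization are counted by arm.

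**3. Other places where worsening could show.**
- Serious events: listed in detail. A listing keeps the event visible but does not compare arms, and non-serious aggravation is outside it.
- Infections (SAP 6.5.3): "an infection will be defined as an Adverse Event with SOC equal to" infections and infestations, described on ITT with no emergence limit. This covers one system organ class.
- Physical examination (SAP 5.2 and 6.6.3): summarized by arm at each visit, but scored normal, abnormal or not evaluated. An abnormal finding that worsens stays abnormal.
- Stool frequency and consistency (SAP 6.5.3): weekly diary summaries, indirect and confined to stools.
- Regurgitation and vomiting: not evaluated (SAP 1.1). Laboratory parameters: not applicable (SAP 6.6.2).

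None of these replaces a worsening clause.

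**4. Size.** Inputs from the documents are 80 infants and 1:1 allocation, so 80/2 = 40 per arm. The share q of infants with a run-in event that worsens on product is not given and is assumed here. Expected number = 80q; chance of at least one = 1 − (1 − q)^80.

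| Assumed q | Expected infants | Chance of at least one |
|---|---|---|
| 1% | 0.8 | 55% |
| 2.5% | 2 | 87% |
| 5% | 4 | 98% |
| 10% | 8 | >99% |

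One infant in an arm is 1/40 = 2.5%. Sample size, alpha and power do not depend on any of this.

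**The case against.** A reader might infer that a run-in condition which worsens on product drops out of the comparison between arms altogether. The documents do not say so. Section 6.6.1 promises events from the whole study, words its by-arm tables for AEs without an emergence limit, and separately reports the frequency of SAEs and of AEs leading to hospitalization. A separate listing of run-in events could simply be an addition. This stands, and it is why the conclusion is *may be left out* and not *is left out*.

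A reader might also infer that the rule makes the product look safer. The same rule applies to both arms, run-in events precede randomization, and no formal safety test is planned. The rule could hide a difference only if worsening on product differed between arms and the tables were confined to emergent events. The documents establish neither.

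A third inference would be to count every infant with a run-in event as affected. If 5% to 15% of 80 had one (an assumption), that would be 4 to 12 infants, but the group concerned is only the part whose event is unresolved at T1 and then worsens. The flow chart marks the eligibility criteria again at T1. The synopsis calls the run-in a pre-enrollment period and excludes fever or infectious disease in the two weeks before enrollment, so on that reading many infectious illnesses of the run-in would prevent randomization. This too stands.

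Finally, the protocol supplied is an English synopsis of a fuller Italian document. A convention for recording worsening may exist there or in the CRF instructions. That is possible, but it would not alter the emergent definition in the SAP, which is the text that the programmer follows.

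**Conclusion.** The point holds in a limited form. Emergence rests on onset date alone, the AE definition covers appearance alone, and neither document supplied brings worsening back in. A run-in condition kept as one record that worsens or becomes serious after the first dose is therefore non-emergent under the stated rule. Whether it is then missing from the by-arm tables is open, because the SAP does not say which of them cover emergent events only. SAEs remain visible in the detailed listing.

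The number affected is probably small and could be zero; the figures above are illustrations under an assumed rate, not estimates. The change is worth making because it replaces a stated rule with a better one at little cost. It does not call the design or the primary analysis into question.

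**What to change.** - **SAP 6.6.1:** define treatment-emergent as onset after the first dose, or a condition present before the first dose that worsens in severity or becomes serious after it.
- **SAP 5.2:** define an AE as the *appearance or worsening* of a sign, symptom or condition.
- **Recording:** state whether a worsening opens a new record with its own date or updates the existing one.
- **Tables:** state which tables are restricted to emergent events, and that the by-arm AE and SAE tables include events that worsened on product. Keep the separate listing for run-in events that did not worsen.

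The cost is a few sentences in the SAP and one programming condition on severity and seriousness. This needs the date of the change to have been captured; where it was not, the SAP should say how such events are classed. The downside is that reported treatment-emergent counts may rise slightly.

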#### **6.6.2. Laboratory parameters**

Not Applicable.

#### **6.6.3. Vital signs/Physical examination**

Physical examination will be summarized by treatment group by means of absolute and relative frequency at each visit.

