Criteria for evaluation	
Primary efficacy variable
 
The primary efficacy variable was the proportion of successful treatments, defined as a 50% or greater reduction in the average daily duration of crying episodes after 28 days of treatment.
 
Secondary efficacy variables
 
 • Decrease from baseline in the number of crying episodes and in the persistence of colics at the end of the study (day 28) • Decrease in the number of regurgitation and vomiting episodes • Number of respiratory, gastrointestinal, cutaneous and urinary infections during the study • Number of bowel movements • Consistency of fecal mass using the Bristol scale • Effects of BB-12 on intestinal microbiota • Variations of the intestinal production of innate immunity peptides (calprotectin, β defensin type 2, LL37) and short-chain fatty acids (butyrate e propionate) 
Safety variables
 
Safety was assessed based on the results of physical exams and on the incidence of adverse events (AE).

Statistical methods	
The following analysis sets were defined:
 
 • Per Protocol Set (PP): all randomized patients who completed the study without any significant protocol violation. • Intention to Treat Set (ITT): all randomized patients who received at least one dose of study treatment. • Safety Set: all randomized patients who received at least one dose of study treatment. 
Patients were analyzed according to the treatment received.

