### **3.2. TREATMENT GROUPS AND RANDOMIZATION**

Enrolled infants are randomized at T1 to Bifidobacterium BB-12® or Placebo.

Randomization is done according to a randomization list obtained by a specific software and provided by the Coordinator Center.

The treatment regimen can be summarized as follows:

- Group I: patients who take Bifidobacterium BB-12® (Bifidolactis Infant), 6 drops a day (guaranteeing a billion of living cells) for 28 consecutive days;
- Group II: patients who take Bifidolactis Infant Placebo 6 drops a day for 28 consecutive days.

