### Physical examination

Physical examination is evaluated at each visit. The following locations will be analyzed, considering if the result was normal, abnormal or not evaluated: hairs/skin, lymph nodes, eyes, ears/nose/throat, breast, respiratory, cardiovascular, abdomen, urogenital, pelvic, rectal, musculoskeletal, neurologic, mental status.

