## 6. DEFINITION AND GENERAL METHODOLOGY

### 6.1. GENERAL METHODOLOGY

All statistical tables, listings and figures will be produced using SAS® for Windows release 9.4 (64-bit) or later (SAS Institute Inc., Cary, NC, USA). Continuous data will be summarized by mean,

	Statistical Analysis Plan
	Sponsor:
	Protocol number:

standard deviation (SD), median, 1st and 3rd quartile, minimum and maximum. Categorical data will be presented by absolute and relative frequencies (n and %) or contingency tables.

Percentages will be computed considering patients with non-missing information, if not differently specified.

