#### DEFINITION OF BASELINE

The baseline period for the present study is defined as visit T0.

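### The planned physical-examination table gives only per-visit frequencies by arm, so it cannot count infants who became abnormal on treatment, and the percentage denominator is undefined

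*SAP*

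**What the plan says.** The Protocol synopsis (Criteria for evaluation) rests safety on two things: physical examinations and the incidence of adverse events. SAP 6.6.2 plans no laboratory parameters.

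SAP 5.2 states that "Physical examination is evaluated at each visit" and lists 14 body sites, each classified by "considering if the result was normal, abnormal or not evaluated". The flow chart in SAP 3.7 marks the examination at all six visits, T0 to T5. SAP 3.2 places allocation at the second of these: "Enrolled infants are randomized at T1 to Bifidobacterium BB-12® or Placebo". Two examinations therefore fall before dosing and four after it.

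The whole analysis plan for these data is the one sentence in SAP 6.6.3: "Physical examination will be summarized by treatment group by means of absolute and relative frequency at each visit". It gives no shift table, no change from a pre-treatment visit and no definition of a new abnormality.

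Two general rules in SAP 6.1 bear on this. On denominators: "Percentages will be computed considering patients with non-missing information, if not differently specified". On baseline: "The baseline period for the present study is defined as visit T0". Section 6.6.3 adds nothing to either.

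**The concern.** The useful safety question is whether infants who were normal at a site before dosing became abnormal on the product more often than on placebo. A table of separate visit totals does not follow individual infants. New findings and resolved findings offset each other within an arm, and repeated findings in one infant look the same as single findings in several.

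The SAP does follow infants over time for its other safety variables. Anthropometric data get changes from T0 (6.6.4), and adverse events are split by onset relative to the start of treatment (6.6.1). Physical examination has neither.

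The second issue is the denominator. *Not evaluated* is a listed result category, but the SAP does not say whether an infant so recorded has non-missing information. Two programmers could produce different percentages from the same data, and one of the two readings lowers the abnormality rate.

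**Working it through.** The documents give no expected abnormality rate and no expected rate of *not evaluated*, so there is no figure of the plan's to reproduce. The counts below are assumptions chosen to show the mechanism. The arm size of 40 comes from 80 infants (SAP 3.6) randomized 1:1 (Protocol synopsis, Methodology).

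**1. What per-visit totals determine.** For one site and one arm, with every infant evaluated at both visits:

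abnormal at T5 − abnormal at T1 = new − resolved

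The table fixes only the difference. Assume 4 of 40 abnormal at T1 and 4 of 40 at T5. The table shows 4/40 = 10.0% at both visits, so new = resolved, and resolved can be at most 4. Among the 40 − 4 = 36 infants normal at T1:

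| New abnormalities | Resolved | Rate among 36 normal at T1 |
|---|---|---|
| 0 | 0 | 0% |
| 1 | 1 | 2.8% |
| 2 | 2 | 5.6% |
| 3 | 3 | 8.3% |
| 4 | 4 | 11.1% |

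All five rows give the same planned output.

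**2. Repeated versus separate findings.** Suppose 1 of 40 infants is abnormal at each of T2, T3, T4 and T5. The table shows 1/40 = 2.5% four times. If it is the same infant, 1/40 = 2.5% were ever abnormal on treatment. If it is four different infants, 4/40 = 10% were.

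**3. Denominator.** Assume 4 abnormal in an arm of 40, with k infants not evaluated at that site. The rate is 4/40 if *not evaluated* stays in the denominator, and 4/(40 − k) if it is treated as missing.

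| k | Kept in: 4/40 | Removed: 4/(40 − k) |
|---|---|---|
| 0 | 10.0% | 4/40 = 10.0% |
| 4 | 10.0% | 4/36 = 11.1% |
| 8 | 10.0% | 4/32 = 12.5% |
| 12 | 10.0% | 4/28 = 14.3% |
| 20 | 10.0% | 4/20 = 20.0% |

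On the first reading, an assumed 10% to 50% not evaluated turns 11.1% to 20.0% into 10.0%. On the second reading there is no dilution. SAP 6.1 does not settle which applies.

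**4. Whether the adverse-event tables fill the gap.** SAP 5.2 defines an adverse event to include an undesirable sign that appears. SAP 6.6.1 calls it treatment-emergent if its onset follows the start of treatment, and lists events between T0 and T1 separately. A new examination finding that is reported as an adverse event would therefore be separated from earlier ones. Neither document says that a new abnormal examination has to be reported in that way.

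**The case against.** Four arguments on the other side deserve weight.

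- **The safety plan as a whole can detect new signs.** The adverse-event definition and the treatment-emergent rule give them a route. This stands in part. A reader might infer from section 6.6.3 that the trial cannot separate new from pre-existing abnormalities at all. The documents do not support that: the limit is in this one output, and the T0 and T1 results are scheduled for collection. A rule requiring abnormal examinations to be reported as adverse events could also sit in the full protocol or the case report form. Only an English synopsis based on the Italian protocol is available, so such a rule can be neither assumed nor excluded.
- **There is a randomized placebo arm.** Randomization balances T1 prevalence in expectation, so on-treatment prevalence can be compared between arms. For equal prevalence to hide a product effect, extra new findings on product would have to be offset by extra resolutions on product, or by a chance imbalance at T1. This stands, but it remains a comparison of prevalence, and in arms of about 40 a chance imbalance at T1 carries into later visits.
- **Dilution is not established.** A reader might infer that *not evaluated*, being a recorded result, must count as non-missing and so lowers the rates. The SAP does not say so; it can equally be read as no information on that site. If all three categories are tabulated with absolute counts, the reader can also recompute the rate. What remains is an undefined rule.
- **The inputs are invented.** This is true, and 11.1% is the upper end of a range that starts at 0%. The infants are to be healthy at entry (SAP 3.3). If few are abnormal at T1, there is little to cancel and the per-visit table comes close to new findings. Nor do the documents say that any listed site is seldom examined in infants of this age.

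**Conclusion.** The point holds in a limited form. For one of the two named safety bases, the single planned output cannot show how many infants normal before dosing became abnormal on treatment. In the assumed example, 10.0% at both visits fits any new-abnormality rate from 0% to 11.1%. The adverse-event route is a partial safeguard on the documents available. The percentage denominator is undefined, so rates may be diluted; that they are diluted is not shown.

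The conclusion about linkage follows from the form of the table and needs no assumed rate. The sizes rest on the assumed counts, on 40 infants per arm and, in the first example, on complete evaluation at both visits. Importance is minor: this is a descriptive safety table, with no effect on the primary analysis, the alpha level or the sample size.

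**What to change.** In SAP 6.6.3, keep the per-visit table and add the following.

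- **Shift table.** For each body site and arm, cross-tabulate the T1 result against the worst result at T2–T5. Worst is abnormal if the infant was abnormal at any of those visits, normal if evaluated at least once and never abnormal, and not evaluated otherwise.
- **Reference visit.** Name T1 explicitly as the last examination before dosing, because SAP 6.1 sets baseline at T0 and a programmer would otherwise use that.
- **New-abnormality percentage.** The numerator is infants normal at T1 and abnormal at any of T2–T5. The denominator is infants evaluated as normal at T1 and evaluated at least once at T2–T5. Infants not evaluated at T1 must stay out of it; otherwise a long-standing abnormality first examined at T2 would count as new.
- **Per-visit percentages.** Base them on infants evaluated at that site and visit, and show *not evaluated* as a separate count.

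The cost is a few sentences of SAP wording and one extra descriptive table from data already scheduled for collection. No new procedure or visit is needed.
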